#### Stable Disease (SD)

SD is defined by:

- Does not qualify for CR, PR, or PD AND
- No new lesions AND
- Stable/improved T2/FLAIR AND
- Stable/improved steroids AND
- Stable/improved clinically

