**Table 3 Criteria for Determination of Response/Progression with PVSRIPO Followed by Pembrolizumab**

Response	Criteria
1. Complete	
 
• Disappearance of all enhancing disease and meets criteria in # 4 below
 

2. Partial	
 
• <math>\geq 50\%</math> reduction of biperpendicular diameter of enhancing disease and meets criteria in # 4 below
 

3. Stable Disease	
 
• Does not qualify for CR or PR above AND,
 
• No increase of biperpendicular diameter of total enhancing disease <math>> 25\%</math>, AND
 
• Meets criteria in # 4 below
 

4. Must be met for all responses above:	
 
• Response persists for <math>\geq 4</math> weeks
 
• Response persists for <math>\geq 8</math> weeks post-discontinuation of bevacizumab (once confirmed off bevacizumab, response duration will be reported as when 1st observed when response 1st noted)
 
• No greater than physiologic steroids (<math>\leq 4</math> mg/day dexamethasone or equivalent) for CR; stable/improved steroids for PR and SD.
 
• Stable/improved clinically
 

Immunoprogression	
 
• Increase in enhancing lesion size (with or without new lesions/enhancement into T2/FLAIR), within 12 mos of PVSRIPO infusion that responds radiographically to steroids (<math>\leq 4</math> mg/day dexamethasone or equivalent) or bevacizumab (<math>\leq 7.5</math> mg/kg q3 weeks) or a combination of both within 3 months of noting appearance of radiographic progression) AND either: 
 
• Absence of significant clinical decline
 
 OR 
 
• If significant clinical decline is present, it is responsive to post-infusion interventions including steroids (<math>\leq 4</math> mg/day dexamethasone or equivalent) or bevacizumab (<math>\leq 7.5</math> mg/kg q3 weeks) or a combination of both within 3 months of radiographic progressive-type appearance (ie, <math>\geq 25\%</math> increase of biperpendicular diameter of enhancing disease/new lesions/worsened T2/FLAIR)
 
 
 

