Progression	
 
• Does not meet criteria for immunoprogression AND
 
• <math>\geq 25\%</math> increase of biperpendicular diameter of enhancing disease from the smaller of baseline or post-infusion nadir (enhancing at baseline plus any new enhancement) and/or worsened T2/FLAIR, confirmed on a subsequent scan performed at least 3 months later (unless clinical deterioration prevents confirmatory scan). If confirmed, progression date is the date that progression was first observed.
 

Investigator reported results may be verified by independent central radiographic reviewers blinded to patient outcome and possibly bevacizumab use. Response will be summarized at

[figure not shown]
 Not inclusive of clinical deterioration clearly due to an intercurrent illness or condition not directly related to the patient's tumor.

regular intervals including those achieving a response by 6, 12 and 24 months post-PVSRIPO infusion.

Given that the NANO scale has been shown to provide a more detailed and objective measure of neurologic function for predicting the prognosis of glioblastoma patients especially at the time of progression [33], the NANO scale will be utilized to explore clinical neurologic function as a correlate of response, especially with regard to immunoprogression and/or confirmed progression, along with KPS.

[figure not shown]
Final criteria for determining response and progression will be outlined in the SAP and the SAP will prevail in the event differences are noted.

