#### Progressive Disease (PD) which must be confirmed as described below

Initial PD by RANO is defined by:

- $\geq 25\%$  increase in the sum of biperpendicular diameters of enhancing disease OR
- New lesions OR
- Significant worsened T2/FLAIR OR
- Significant clinical decline

Confirmation of progression on follow-up imaging 3 months after initial radiographic progression is required in the following situations

- No new or significantly worsening neurologic deficits not due to co-morbid event or concurrent medication AND
- $\leq 6$  months from initiation of immunotherapy

If follow-up imaging confirms progression, the date of actual progression should be backdated to the date of initial radiographic progression. Also note that the appearance of new lesion solely does not define progressive disease if they occur  $\leq 6$  months from initiation of immunotherapy. Rather the lesions are added to the total lesion areas for follow-up assessments.

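### Under the SAP, an early asymptomatic increase of 25% or more with no confirming scan falls into stable disease by default

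*SAP*

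**What the plan says.** SAP 3.2.6 defines SD by exclusion: "Does not qualify for CR, PR, or PD AND", then no new lesions, "Stable/improved T2/FLAIR AND" the same stability requirement for steroids and clinical status. Tumour size enters only through the exclusion of PD.

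The PD entry is headed "Progressive Disease (PD) which must be confirmed as described below". Under it, initial PD includes a 25% or greater "increase in the sum of biperpendicular diameters of enhancing disease OR" one of three other findings: new lesions, significant T2/FLAIR worsening, or significant clinical decline. Then: "Confirmation of progression on follow-up imaging 3 months after initial radiographic progression is required in the following situations". Two conditions must both hold: no new or significantly worse neurologic deficit, and no more than 6 months since immunotherapy began. The SAP backdates PD if the later scan confirms it, and gives no rule for a scan that is never obtained.

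SAP 3.2.3 imputes missing data only where it says so, and response is not mentioned. SAP 5.7.1.2 tabulates best overall response as CR, PR, SD and PD, with no row for unconfirmed or non-evaluable cases.

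Protocol Table 3 (Section 8.4.6.1) handled both matters differently. Its SD carries an explicit limit, "No increase of biperpendicular diameter of total enhancing disease" above 25%, and its progression rule requires a confirming scan "unless clinical deterioration prevents confirmatory scan". The SAP sets Table 3 aside (3.2.6 and Section 6) and, under Protocol Section 8, the SAP governs.

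**The concern.** SD is a leftover category and PD is conditional on a second scan. A participant whose tumour grew, and who then withdrew, died or changed therapy before that scan, is therefore not PD and can satisfy the SD conditions. The default is the favourable category, and it applies to people whose tumour grew and whose imaging stopped.

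Two outputs are exposed: the SD and PD rows of Table 14.2.1.1, and DCR, a secondary endpoint. The trial is open-label and single-arm, and SAP Section 6 reports that central imaging review was not completed. No independent read would settle these cases, so the written rule has to.

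**Working it through.** The plan gives no figure for SD or DCR. Its only computed design figure is ORR power, which reproduces: an exact binomial test with n=30, 11% against 31% and rejection at 8 or more responders has upper-tail alpha 0.0135 and power 0.757, against the stated figure of more than 75%. It is not at issue here, because SD and PD are both non-response.

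**Step 1: apply the SAP rules to a 25% or greater increase.**

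| Situation | PD? | SD? | Result |
|---|---|---|---|
| Up to 6 months; no new or worse deficit; no new lesion; T2/FLAIR, steroids and clinical status stable; no confirming scan | No | Yes | SD |
| As above, but confirming scan done and positive | Yes, backdated | No | PD |
| As above, but first seen after 6 months | Yes, at once | No | PD |
| New or significantly worse deficit, any time | Yes, at once | No | PD |
| Up to 6 months; no deficit; but worse T2/FLAIR, a new lesion or more steroids; no confirming scan | No | No | No category |

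The first row is the gap. The last row shows that other unconfirmed cases have no place in the table at all.

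**Step 2: who can fall into the first row.** Nominal MRIs are at Weeks 5, 8 and 11, then every 9 to 12 weeks (SAP Table 1, footnote 13): 11+9=20 and 20+9=29, or 11+12=23 and 23+12=35. Six months is 182.6/7=26.1 weeks from infusion. The SAP does not say whether initiation of immunotherapy means the infusion or the first pembrolizumab dose. With the latter, the window closes at 26.1+2=28.1 or 26.1+4=30.1 weeks. A first dose at Week 4 also shifts the schedule by 2 weeks, so the scan falls at Week 31 or 37. Either way, a participant who stays in imaging has a nominal scan outside the window, and growth still present there is PD. The gap is left for participants whose imaging stops early, or whose later scans, on another therapy, no longer show the growth.

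**Step 3: effect on best overall response.** A participant already SD on an earlier scan may keep SD as best response whatever happens next. The effect is clearest when the first follow-up scan already shows growth.

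**Step 4: effect on DCR.** If imaging stops before 6 months, SD of 6 months or more is not documented by imaging. DCR is inflated only if SD duration runs to last contact, or if scans on new therapy count. The SAP excludes neither. It does not define where the SD interval starts or ends. The rule making new cancer treatment a failure (SAP 5.7.1.1) is written for ORR, and the DCR text (5.7.2.1) refers to 5.7.1.2 instead. Protocol 5.4 and 5.5 keep participants in follow-up, with MRIs, after other therapy starts.

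**Step 5: size per participant.** 1/30=3.3 points. SAP Section 6 says full enrolment was not reached; at an assumed n=20 it is 1/20=5 points. As an illustration with assumed counts and Clopper-Pearson 95% intervals, 6/30 is 20.0% (7.7 to 38.6), 7/30 is 23.3% (9.9 to 42.3) and 9/30 is 30.0% (14.7 to 49.4).

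**The case against.** The strongest reply is that the SAP does limit growth: SD excludes PD, and PD starts at a 25% increase. That stands as far as it goes. A reader might infer from the SD text alone that any asymptomatic tumour that grew is scored as stable. The documents do not support that. Growth after 6 months, or with a new or significantly worse deficit, is PD at once, and the other SD conditions remove more cases. The limit fails only when PD awaits a scan that never comes. The SAP also does not say outright whether PD inside the SD definition means initial or confirmed PD. However, it separates the two and says PD must be confirmed, so SD is the literal result.

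A second reply is that the Table 3 waiver for clinical deterioration was not really lost. Most of it survives. A new or worse deficit removes the need for confirmation, and SD requires stable clinical status. Participants who visibly deteriorate are not the ones who slip into SD.

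A third reply is that later scans, and the treatment of new therapy as failure, protect DCR. The first part holds for participants who stay in imaging without new therapy. The second is arguable, because DCR is to be analysed similarly to ORR, but the cross-reference does not reach the estimand section.

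Finally, the protocol's opening notice warns that treatment-related enlargement can persist for 6 months or more. Forcing every unconfirmed case to PD would mislabel some of these, so a separate non-evaluable row is equally defensible.

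**Conclusion.** The point holds for a narrow group: growth of 25% or more within 6 months of starting immunotherapy, every other SD condition met, and no confirming scan. For that group the SAP's literal result is SD, and no other best-response category is available. The SD row can be too high and, under the conditions in Step 4, so can DCR. ORR is unaffected and the analyses are descriptive, so this is a modest defect, but one worth closing because the default is favourable.

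The size is 3.3 points per participant at n=30, and more with fewer enrolled. The number of such participants cannot be derived from the documents. A reader might try to derive it from the protocol's median survival of 6 to 10 months: with an exponential curve, 1-2^(-3/6)=29.3% and 1-2^(-3/10)=18.8% die within a 3-month wait. Those are probabilities of death in a general recurrent glioblastoma population, not of being scored SD. Many deaths follow a documented decline that is PD or fails SD. Nor does a death within 3 months of growth at Week 11 reach 6 months of SD (11+13=24 weeks).

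**What to change.** Change SAP 3.2.6 and 5.7.1.2 as follows.

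- **SD definition:** add a requirement of less than a 25% increase in summed perpendicular diameters of enhancing tumour, measured against the same reference scan as PD. The SAP names no reference scan, so it must state one. Table 3 bars increases above 25%; a limit below 25% meets the SAP's PD threshold without a gap.
- **Missing confirming scan:** state that initial PD without a confirming scan is neither SD nor disease control. Report it either as PD on the date first seen, or in a separate row for unconfirmed PD or not evaluable that stays in the denominator.
- **DCR:** state that scans taken after other anticancer therapy begins do not count toward 6 months of SD.

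The same edit should define the start and end of the SD interval and the date on which immunotherapy begins, and say how a follow-up scan that does not confirm PD affects SD status.

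The cost is a few sentences and no new data. SD and DCR may come out slightly lower, and a few true immunoprogressions without a follow-up scan will not count as disease control.

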#### Progressive Disease (PD) which must be confirmed as described below

Initial PD by RANO is defined by:

- $\geq 25\%$  increase in the sum of biperpendicular diameters of enhancing disease OR
- New lesions OR
- Significant worsened T2/FLAIR OR
- Significant clinical decline

Confirmation of progression on follow-up imaging 3 months after initial radiographic progression is required in the following situations

- No new or significantly worsening neurologic deficits not due to co-morbid event or concurrent medication AND
- $\leq 6$  months from initiation of immunotherapy

If follow-up imaging confirms progression, the date of actual progression should be backdated to the date of initial radiographic progression. Also note that the appearance of new lesion solely does not define progressive disease if they occur  $\leq 6$  months from initiation of immunotherapy. Rather the lesions are added to the total lesion areas for follow-up assessments.

#### Objective Response Rate (ORR)

ORR is defined as the proportion of participants achieving CR or PR based on iRANO criteria.

#### Duration of Response (DOR)

DOR is defined as time from objective response (CR or PR per iRANO criteria) until confirmed PD or death; censoring at the date of the last imaging without confirmed PD prior to the date the subject is considered off study.

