## **5.5 Follow-Up Period of Off Study Participants/Patients Permanently Discontinuing Pembrolizumab**

If a patient permanently discontinues pembrolizumab prior to or at Week 11, they should report to the clinic as scheduled for follow-up as noted in **Table 1**.

Patients who no longer meet the criteria for the per protocol population (see **Section 8**) or patients who permanently discontinue pembrolizumab for confirmed progression or irAE requiring permanent discontinuation after Week 11 will remain in follow-up, where assessments will occur as outlined in the SOA noted in **Table 1**. However, the frequency should occur per SOC (ie, approximately every 9 weeks), as feasible.

Entry of all applicable data and uploading of scans should occur no later than every 3 months. If SOC follow-up occurs less frequently (ie, greater than 3 months between visits/phone call), data should be transmitted within 2 weeks ( $\pm$  1 week) of acquisition.

Data to be entered in the eCRF during this period may include, but is not limited to the following:

- Patient status: deceased or alive
- Use of additional anti-cancer therapies and/or concomitant medications used to manage PVSRIPO-related inflammation (ie, corticosteroids, bevacizumab) and/or adjustments to such therapies since the last entry.
  - Entries should include start/stop date, dose, route, and frequency.
- MRIs conducted per SOC
  - Any SOC MRIs (deidentified) may be requested by the Sponsor or Sponsor designee. For all SOC MRI, the assessment of tumor size, volume, and other characteristics should be recorded on the eCRF no less than every 6 months as well as in the event of disease progression.
- Neurosurgical procedures required for reasons other than tumor progression (ie, for managing hydrocephalus) since last visit and details of these procedure(s).

Results of any molecular, genetic, or histologic testing from all biopsies/tissue obtained since last recorded entry.

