## **7.2 Serious Adverse Events**

An SAE is any AE meeting the following criteria:

Death	An AE that results in death (note: death due to progression is not an AE/SAE but should be reported as noted in the eCRF completion guidelines).
-------	--

Life-threatening AE	An AE that places the participant, in the view of the Investigator, at immediate risk of death from the AE as it occurred (ie, does not include an AE that had it occurred in a more severe form, might have caused death).
Required or prolonged participant hospitalization	An AE that results in an initial participant hospitalization or prolongs an existing hospitalization of the participant. If a participant is hospitalized as part of the clinical use of the study treatment, the period of normal hospitalization will be based on the Investigator's judgement and experience. Hospitalizations longer than this period will be considered prolonged hospitalizations.
Persistent or significant disability/incapacity	An AE that results in a substantial disruption of a participant's ability to conduct normal life functions.
Congenital anomaly/birth defect	A congenital anomaly/birth defect that occurs in the offspring of a participant exposed to the study drug.
Important medical event	An AE that may not result in death, be life-threatening, or require hospitalization may be considered an SAE when, based upon appropriate medical judgment, the event may jeopardize the participant and may require medical or surgical intervention to prevent 1 of the outcomes listed above. Examples of such "important medical events" include allergic bronchospasm requiring intensive treatment in an emergency room or at home, blood dyscrasias or convulsions that do not result in participant hospitalization, or the development of drug dependency or drug abuse

SAEs must be reported by the Investigator to the Sponsor or designee within 24 h of discovery for all patients from the time of consent, while on study and for 30 days after 1) completion of study participation or 2) if patient is rendered off-study and in the follow-up period only. SAEs will be reported in the eCRF with instruction provided in the eCRF Completion Guidelines.

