## 8 Statistical Analyses

This single-arm study is designed to evaluate the efficacy, safety and tolerability of PVSRIPO when followed by pembrolizumab treatment in patients with rGBM. Summary statistics (eg, n, %, CI) will be employed to describe the key findings (ORR, DOR, incidence and severity of DLT, Grade 3 or higher AE, etc.).

Adverse events considered related to screening or other pre-infusion procedures that are not standard of care (eg, PV booster, biopsy prior to infusion, catheter placement without PVSRIPO infusion) will be summarized separately from TEAE (after PVSRIPO infusion), as will data from patients receiving only PVSRIPO and not at least one dose of pembrolizumab. The number of doses of pembrolizumab received and other baseline characteristics will also be explored as variables for safety and efficacy (eg, age, number of prior recurrences, baseline NANO and KPS, extent of prior resection, prior bevacizumab and chemotherapy use, tumor genetic profile).

All patients enrolled and treated with PVSRIPO will be summarized in all analyses. In addition, a per-protocol analysis will also explore the impact of excluding patients meeting pre-defined criteria from radiographic and survival analyses as outlined in [Section 8.4.6](#). For comparisons of efficacy or safety relative to PVSRIPO alone or pembrolizumab alone from other data sources, both the overall and per-protocol populations may be considered.

In general, patients should follow the protocol treatment plan outlined and will be considered on study if there are no major protocol deviations including prohibited tumor-treatments, until the time of confirmed disease progression, or until the investigator and/or patient feel it is in the patient's best interest to stop study treatments or study participation.

The SAP, which will be finalized before conducting the analyses, will present details about planned statistical summary methods and analyses. A brief summary of the SAP is provided below by section. The SAP will govern in the event the protocol and the SAP differ.

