#### **8.4.6.2 Duration of Response and Durable Radiographic Response**

The DOR is defined as time from first confirmed response until confirmed PD or death, whichever comes first.

A DRR is defined as a radiographic response that persists for  $\geq 6$  months.

The DOR and DRR for those meeting the criteria for confirmed response (CR or PR) with and without those achieving SD will be calculated. Endpoints as evaluated by iRANO and inclusive of SD will be utilized to describe these endpoints for overall DCR.

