#### 5.7.1.1. Statement of Estimand

The **population for the trial** is defined through appropriate inclusion/exclusion criteria (IC/EC) to reflect the targeted participant population for approval. The analysis population is based on the efficacy analysis set.

The **treatment** of interest is lerapoltrev + pembrolizumab.

The **variable** of interest for ORR is the binary response value for a participant. For DOR, the variables of interest are the time from first response to confirmed progression/death/censoring.

The ability to evaluate treatment effect using the variables may be impacted by **intercurrent events** (ICEs). Death and use of additional cancer treatments may all impact the interpretation of treatment effect. For ORR, a composite strategy will be used to address intercurrent events (ICEs)

of potential death and start of additional cancer treatments, meaning occurrence of any of these events prior to a participant achieving CR or PR will mean the participant is considered a non-responder. DOR will use a composite strategy as well, treating death as an event that ends response, and the start of additional cancer treatments medications will be censored under the strategy.

The **population level summary measures** are the ORR, and the Kaplan Meier (KM) estimated median DOR, and associated CI for treatment.

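### The SAP censors duration of response at an undefined off-study date, which conflicts with its own estimand and on one supported reading drops progression and deaths the trial collects

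*SAP*

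**What the plan says.** SAP 3.2.6 gives the endpoint as follows: "DOR is defined as time from objective response (CR or PR per iRANO criteria) until confirmed PD or death". The censoring rule attached to this definition is "censoring at the date of the last imaging without confirmed PD prior to the date the subject is considered off study". It does not mention new cancer therapy and does not define *off study*.

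SAP 5.7.1.1 states the DOR estimand as "treating death as an event that ends response, and the start of additional cancer treatments medications will be censored under the strategy". Death and additional cancer treatment are the only intercurrent events it names. Stopping study treatment is not one of them, and there is no off-study cut-off.

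The protocol's definition (8.4.6.2) has no censoring rule: "The DOR is defined as time from first confirmed response until confirmed PD or death, whichever comes first".

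The protocol uses the status in several ways:
- Section 8 says that patients "will be considered on study if there are no major protocol deviations including prohibited tumor-treatments, until the time of confirmed disease progression". A judgment by either party, doctor or participant, can also close the status, and the wording covers two kinds of stop: "best interest to stop study treatments or study participation".
- Section 7.1.3 pairs coming off study with no longer meeting the per-protocol requirements.
- Section 5.5 is headed "Follow-Up Period of Off Study Participants/Patients Permanently Discontinuing Pembrolizumab" and collects vital status, MRIs and later therapies.
- Section 7.2 has a safety-reporting period that applies "if patient is rendered off-study and in the follow-up period only".
- Section 5.4 expects all treated participants to remain in the study for long-term follow-up, whether or not they stop study treatment or add other therapy.

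**The concern.** A censoring date for a primary endpoint has to be one that two programmers would derive identically, and this one is not. If *off study* can mean the day study treatment stops, responders can be censored while they are still being scanned and followed for survival. Progression or death that the trial goes on to record would then be left out of the DOR analysis. Stopping may also be related to prognosis, in which case the censoring is informative.

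The set is small. At the planned 30 patients, the null and target response rates give 0.11 × 30 = 3.3 and 0.31 × 30 = 9.3 responders. SAP 6 says the full sample was not enrolled, so at those rates there would be fewer. Each event bears heavily on a Kaplan–Meier median from so few patients.

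**Working it through.** The plan states no DOR figure to reproduce. Its only design figure, power above 75%, concerns ORR. The check is therefore a comparison of the rules, followed by an illustration.

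**Step 1. Three readings of *off study*.**
- A: study treatment stops by a best-interest decision, or a major deviation occurs (Protocol 8; 7.1.3 with the per-protocol exclusions in 8.4.6).
- B: non-study tumor treatment starts (Protocol 5.3.4, which explains leaving the per-protocol population in those terms).
- C: study participation ends (Protocol 5.4; SAP 3.2.6 measures days on study to the End of Study eCRF page).

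**Step 2. Apply them to hypothetical patients.** Each responds at month 12 and stops study treatment on a best-interest decision at month 14.

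| Patient | 3.2.6, reading A | 3.2.6, reading B | 3.2.6, reading C | SAP 5.7.1.1 |
|---|---|---|---|---|
| PD on follow-up MRI, or death, at month 17; no new therapy | censored at ≤ 14 − 12 = 2 months | event at 17 − 12 = 5 months | event at 5 months | event at 5 months |
| New cancer therapy at month 15; PD at month 17 | censored at ≤ 2 months | censored at ≤ 15 − 12 = 3 months | event at 5 months | censored at ≤ 3 months |

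Reading A conflicts with the estimand for the first patient. Reading C conflicts with it for the second, because 3.2.6 omits censoring at new therapy. Only reading B broadly reproduces 5.7.1.1, and the SAP does not say that B is meant.

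Backdating in SAP 3.2.6 protects progression first seen before the off-study date and confirmed later. It does not protect progression first seen on a later follow-up scan.

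**Step 3. Illustrate the size (A against C).** None of these inputs is in the documents except the scan spacing, which approximates the 9–12 weeks planned after Week 11:
- exponential DOR with on-treatment median 6, 9 or 12 months;
- exponential time to stopping with median 6 or 12 months;
- hazard after stopping multiplied by k = 1, 2 or 3;
- 18 months of follow-up after response, and scans every 2.5 months;
- 200,000 simulated responders, with no new therapy.

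Under A, the patient has an event if T ≤ stop; otherwise the patient is censored at 2.5 × floor(stop/2.5). Under C, all events up to 18 months count.

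| On-treatment median, stopping median, k | Median under C (events) | Median under A (events) | A − C |
|---|---|---|---|
| 6, 12, 1 | 6.0 (87%) | 5.6 (64%) | −0.4 |
| 12, 6, 1 | 12.0 (65%) | 10.3 (32%) | −1.7 |
| 6, 6, 2 | 5.0 (95%) | 5.2 (49%) | +0.2 |
| 12, 6, 3 | 7.6 (86%) | 10.4 (32%) | +2.8 |

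These rows span the shifts over all 18 combinations: 0.4–1.7 months shorter when stopping is unrelated to prognosis (k = 1), and 0.2–2.8 months longer when the hazard doubles or triples. Events are seen in 32–64% of responders under A and 65–97% under C.

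The downward shift arises because the simulation dates events exactly but moves censoring back to the last scan. It applies to deaths and to progression found between scheduled scans. Where progression is dated only to scheduled scans, the shift largely disappears.

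**The case against.** The best defence is that *off study* was never meant to cover everyone who stops treatment. Section 5.4 makes remaining in the study the default. Section 5.3.4 equates leaving the per-protocol population with starting non-study tumor treatment. The SAP uses post-study in the same sense for later systemic therapy and radiotherapy (5.3 and the listings in 10). On that reading 3.2.6 and 5.7.1.1 largely agree. The censoring clause can also be read as applying only to patients with neither PD nor death. And since Protocol 8.4.6.2 has no censoring rule and Section 8 lets the SAP govern, the absence of this cut-off from SAP 6 proves little.

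Most of this stands as a limit on the claim. It does not remove the problem: these readings compete with Section 8 and Section 7.1.3, and the SAP selects none of them.

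A reader might infer three stronger things that the documents do not support:
- *That the protocol makes every patient who stops treatment off study.* Section 8 refers to a best-interest decision, the Section 5.5 heading joins two groups with a slash, and Section 5.4 points the other way. A stop for an immune-related event is part of the treatment plan, so it is a disputed case.
- *That events are certainly discarded.* This depends on the reading adopted.
- *That median DOR is inflated, perhaps doubled.* Censoring half of responders exactly 1 month before PD takes a 12-month median to 23.3 months in simulation, but no document supports that pattern. Follow-up also stops at 24 months. On the Phase 1 response times (median 15.4 months, earliest 5.7), that leaves 24 − 15.4 = 8.6 months for the median responder and 24 − 5.7 = 18.3 for the earliest, so such a median could not be observed.

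**Conclusion.** The concern holds as an inconsistency in the rule for a primary endpoint. The censoring date rests on an undefined term that the protocol uses in conflicting ways, and 3.2.6 and 5.7.1.1 state different rules. On the Section 8 and 7.1.3 reading, progression and deaths after a treatment stop or major deviation without new cancer therapy are not counted, contrary to the estimand. Where new tumor treatment is what takes the patient off study, the two rules broadly coincide.

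The documents fix neither the size nor the direction of any bias. The median tends upward if stopping signals decline, and can move somewhat downward if it does not. The figures of 2.8 months longer and 1.7 months shorter are the extremes of an illustration, not estimates for this trial. The loss of events on reading A is in one direction and falls on a small responder set. DOR is summarised descriptively with no stated test, so what is at stake is the reported median and its interval. The change should be made. Confidence is high on the inconsistency and moderate at most on its numerical effect.

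**What to change.** In SAP 3.2.6, replace the off-study clause with censoring at the last evaluable scan without confirmed PD before the earlier of (i) the start of additional cancer treatment and (ii) the End of Study/last contact date. State that confirmed PD and death after study treatment stops, but before any new cancer therapy, count as events. Put the identical rule in 5.7.1.1.

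The cost is a short text change and a small change to the DOR derivation. No new data are needed, because Protocol 5.5 already collects vital status, MRIs and later therapies. The sponsor should accept that median DOR may come out shorter.
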